14. STUDY TREATMENT COMPLIANCE

Compliance to study treatment and tiotropium will be summarized and listed for the SAF.

14.1. Derivations

Treatment compliance will be summarized by treatment group in 2 ways:

- $100 * ((\text{total number of vials dispensed} - \text{total number of vials returned}) / (\text{expected number of vials to be taken during the study}))$
- Drug intake as recorded in the e-diary: percent of 'yes' responses. The denominator is the number of records for which the patient provided an answer (Yes or No) to drug intake questions (morning and evening) in the e-diary.

15. E-DIARY COMPLIANCE

Compliance to e-diary will be summarized and listed for the SAF.

15.1. Derivations

E-diary compliance for study treatment will be summarized by treatment group, for the duration of the treatment, as per the following:

$100 * ((\text{total number of e-diary entries for study treatment}) / (\text{expected number of e-diary entries for study treatment during the study}))$

Each patient should have a morning and evening dose, which should be recorded in the e-diary, including the dosing at site visits, however only dosing not at the site visit will be included in the compliance calculation. At Week 4 visit there should only be morning dose recorded.

Number of e-diary entries will be calculated as per the following:

$[(\text{reference end date} - \text{reference start date}) * 2 - 1 \text{ evening dose}] - \text{expected number of CRF entries}$

The 1 evening dose will be subtracted for the completed patients.

Expected number of CRF entries for study treatment during the study will be 5 for all patients that have completed the study. In cases where patient discontinues early the following strategy explained below will be used.

1. Count how many entries there are in the "Drug Exposure" CRF dataset.
2. Select how many site visits patient should have based on the following window for each visit:
 - a. Calculate reference end day = reference end date - reference start date + 1
 - b. 0 site visits if reference end day is missing
 - c. 1 site visit if $1 \leq \text{reference end day} \leq 7$

Document: ...\\Verona_Pharma\\RPL554\\BZA48916\\Biostatistics\\Documentation\\SAP\\Verona CO-205 SAP v1.0

Author: [REDACTED] Version Number: V1.0

Version Date: 05DEC2019

Template No.: CS_TP_BS016 Revision 5

Reference: CS_WI_BS005

Effective Date: 01Apr2018

- d. 2 site visits if $8 \leq \text{reference end day} \leq 14$
- e. 3 site visits if $15 \leq \text{reference end day} \leq 21$
- f. 4 site visits if $22 \leq \text{reference end day}$

3. Choose the minimum number between points 1 and 2.

16. EFFICACY OUTCOMES

16.1. Primary Efficacy

16.1.1. Primary Efficacy Variables & Derivations

The primary endpoint is the change from baseline FEV_1 to peak FEV_1 (maximum value following dose during the first 3 hours) at Week 4 (after 4 weeks of treatment).

16.1.2. Primary Analysis of Primary Efficacy Variables

Peak FEV_1 will be summarised as actual value at Week 4 and change from baseline FEV_1 to peak FEV_1 at Week 4 using descriptive statistics for all treatment groups.

Peak FEV_1 will be computed as the maximum value in the 3 hours after dosing. Baseline FEV_1 is the latest measurement taken before study drug on the day of first dosing, i.e. 30 minutes pre-dose at Day 1.

The primary objective of this study is to test the hypothesis that there is a difference between different dose levels of study treatment (RPL554) in comparison with placebo, all administered by nebulizer and added on to tiotropium. The change from baseline FEV_1 to peak FEV_1 will be compared between the treatments using a mixed model for repeated measures (MMRM) with fixed effects for treatment, visit and treatment by visit interaction, patient as random effect and baseline as covariate. An unstructured covariance structure will be used to model the within-patient errors. If the model does not converge a compound symmetry covariance structure will be used. Kenward-Roger method will be used to estimate the model degrees of freedom.

Treatment comparisons will be summarised using mean effect differences with 95% CI and associated 2-sided p-values.

Firstly, RPL554 treatments will be compared to placebo using a closed testing procedure. The testing will begin with the highest dose (3 mg) compared to placebo. If found statistically significant then the lower dose (1.5 mg) will be compared to placebo. If found significant then the next lower dose will be compared to placebo until either all doses are compared to placebo, or a result is found to be non-significant and therefore the comparison ends. Secondly, the doses will be compared in a pairwise fashion as shown in Table 2, below.

Document: ...\\Verona_Pharma\\RPL554\\BZA48916\\Biostatistics\\Documentation\\SAP\\Verona CO-205 SAP v1.0

Author: [REDACTED] Version Number: V1.0

Version Date: 05DEC2019

Template No.: CS_TP_BS016 Revision 5

Reference: CS_WI_BS005

Effective Date: 01Apr2018

Table 2: Pairwise comparison between the RPL554 treatment groups:

RPL554 dose	[REDACTED]	[REDACTED]	[REDACTED]	[REDACTED]	[REDACTED]	[REDACTED]
	[REDACTED]	[REDACTED]	[REDACTED]	[REDACTED]	[REDACTED]	[REDACTED]
	[REDACTED]	[REDACTED]	[REDACTED]	[REDACTED]	[REDACTED]	[REDACTED]
	[REDACTED]	[REDACTED]	[REDACTED]	[REDACTED]	[REDACTED]	[REDACTED]
0.375 mg	[REDACTED]	[REDACTED]	[REDACTED]	[REDACTED]	[REDACTED]	[REDACTED]

The primary efficacy analysis will be performed on the FAS set. The analysis will also be repeated for the subgroups specified in Section 7.4.

A bar chart to present the least squares mean change from baseline FEV₁ to peak FEV₁ for Day 1, Weeks 1 to 4 (based on the MMRM analysis) will be created.

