3.2 Discussion of Study Design, including the Choice of Control Groups

This study aims to determine the effect of RPL554 on the lung function, symptom improvement and safety measures on symptomatic patients with COPD on a stable background of tiotropium.

Twice daily nebulized doses of RPL554 or placebo will be administered for 4 weeks on top of open-label tiotropium. Prior studies have demonstrated that twice daily dosing is appropriate given sustained bronchodilation observed over 12 hours. The treatment duration should allow for evaluation of RPL554 as a maintenance bronchodilator, including peak FEV₁, and the anti-inflammatory response associated with the PDE3/4 dual mechanism of action, as measured by trough FEV₁ and improvement in symptoms. An equal number of reversible and non-reversible patients is planned in order to enrich the population with patients expected to be more responsive to bronchodilator treatment to support optimal dose selection.

A parallel group placebo-controlled design is used to allow for an examination of any dose dependent effects on efficacy and safety compared to placebo. This design makes it possible to obtain unbiased inferences about differences between treatments. Treatments will be administered double-blind with the Investigator and patient unaware of the treatment identity to further minimize any potential bias in the overall assessment of treatment effect and safety.

An eight-fold dose range has been selected in order to show a separation between efficacious and sub-optimal doses.

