5.7 Method of Assigning Patients to Treatment Groups

All patients consented will be assigned a patient identification number upon signing of the informed consent using the following convention: XXX-YYY where XXX is the center number and YYY is the patient number (001, 002, etc.).

Patients will be stratified at randomization according to reversibility testing at Screening, such that all treatment groups will have approximately equal numbers of patients who are reversible to albuterol ($\geq 12\%$ and ≥ 200 mL increase in FEV₁) and those who are not. Each stratum will be capped at 50%. Within each stratum, patients will be equally randomized to one of the four doses or placebo before the first study medication administration at Visit 2. Medication identification numbers will be provided on the study medication kit.

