The peak effect on FEV₁ will be computed as the maximum value in the 3 hours after dosing. The average effect will be calculated as the AUC divided by the length of the time interval of interest. For analysis, the peak, average and trough FEV₁ will be included as the change from the pre-dose Day 1 baseline value.

Computed pharmacodynamic parameters based on FEV₁ will be compared between the treatments using a mixed model for repeated measures (MMRM) with fixed effects for treatment, visit and treatment by visit interaction, baseline as covariate, patient as random and covariance structure by visit.

RPL554 treatments will be compared to placebo using a closed testing procedure. The highest dose (3 mg) will first be compared to placebo, and if found statistically significant then the next dose (1.5 mg) will be compared to placebo, and so on. Secondarily, doses will be compared pairwise. Results of the comparisons will be expressed as the mean effect difference with 95% confidence intervals and associated, 2-sided, p-value.

Pharmacodynamic parameters based on FVC, average daily use of rescue medication, average weekly E-RS™:COPD means, SGRQ-C, TDI, CAT and PGAC scores will be compared between the treatments using similar MMRM models as for the primary variable. Subdomain scores of the E-RS™:COPD, SGRQ-C and weekly morning symptoms and activity limitation will be summarized and subjected to exploratory analyses.

The number of COPD exacerbations will be summarized by treatment group.

As a sensitivity analysis the primary endpoint (peak FEV₁ at Visit 6), the average AUC_{0-12h} FEV₁ at Visit 6 and the total E-RS™:COPD score at week 4 will also be compared using analysis of covariance (ANCOVA) models with fixed factors for treatment, reversibility strata and the pre-dose baseline value as a covariate.

9.4.6 *Pharmacokinetics*

Plasma concentrations of tiotropium and RPL554 will be summarized by dose level using descriptive statistics (n, geometric mean, coefficient of variation, arithmetic mean, standard deviation, minimum, maximum and median).

9.4.7 *Safety*

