7. STATISTICAL CONSIDERATIONS

7.1. Adjustments for Covariates and Factors to be Included in Analyses

The following covariates and factors will be used in the analyses. For details of their inclusion in the models, see the specific analysis section.

- Fixed effects: treatment (RPL554 0.375 mg, RPL554 0.75 mg, RPL554 1.5 mg, RPL554 3 mg, Placebo), visit (Day 1, Weeks 1, 2, 3 and 4), visit*treatment, actual reversibility strata (reversible, non-reversible)
- Random effect – patient
- Covariate – baseline

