16.2.2. Analysis of Secondary Efficacy Variables

PD parameters (trough FEV₁, peak FEV₁, FEV₁ AUC_{0-T}, trough FVC, peak FVC and FVC AUC_{0-T}), rescue medication, average weekly E-RSTM:COPD, SGRQ-C, TDI and PGAC scores will be analysed using an MMRM approach, as described in Section 16.1.2 for the primary endpoint. The change from baseline will be analysed for all endpoints except TDI and PGAC. The BDI will be used as baseline for TDI. The baseline term will not be included in the MMRM analysis of PGAC.

For exploratory purposes, the subdomain scores of E-RSTM:COPD and SGRQ-C will also be summarised and analysed in the same way.

A plot of the mean change from baseline FEV₁ to each post-dose FEV₁ result over time will be created by visit and treatment group.

The number of patients experiencing at least one COPD exacerbation and the number of exacerbations will be summarized by treatment group.

Individual questions for E-RS and SGRQ-C questionnaires will be listed.

A plot of the least squares means change from baseline to total score E-RS over time will be presented (based on the MMRM analysis).

Furthermore, an analysis of the proportion of responder patients, with an improvement from baseline in SGRQ-C total score of 4 or more, will be summarised by visit and treatment group and analysed using logistic regression. The model for each visit will include randomised treatment groups and actual reversibility strata as factors. Patients with a missing response, either due to withdrawal or that the SGRQ-C questionnaire was not filled in properly, will be assumed to be a non-responder.

A bar chart of the percentage of responders at each visit will also be presented by treatment group.

Total score will be used for the TDI analysis; BDI and TDI total and subdomain scores will be listed.

The secondary efficacy analyses (excluding the PK summaries) will be performed on the FAS set. The PK results will be summarised for the PKS set.

The analyses of the secondary safety endpoints are described in Section 17.

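### The primary MMRM, and the MMRMs that refer to it, leave out the reversibility stratum used at randomisation; if the stratum predicts peak FEV1 change beyond baseline, standard errors are too large and tests conservative

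*SAP*

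**What the plan says.** Protocol 5.7 fixes the design: "Patients will be stratified at randomization according to reversibility testing at Screening", with each stratum capped at 50% and equal allocation to the five arms within stratum. Protocol 3.2 explains that equal numbers of reversible and non-reversible patients are meant to "enrich the population with patients expected to be more responsive to bronchodilator treatment".

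The primary model in SAP 16.1.2 has "fixed effects for treatment, visit and treatment by visit interaction, patient as random effect and baseline as covariate". Protocol 9.4.5 lists the same terms: "fixed effects for treatment, visit and treatment by visit interaction, baseline as covariate, patient as random and covariance structure by visit". Neither includes the stratum. SAP 16.2.2 states that the secondary endpoints "will be analysed using an MMRM approach, as described in Section 16.1.2 for the primary endpoint", and SAP 16.3.2 does the same for the exploratory MMRMs.

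SAP 7.1 reads differently. Its list of fixed effects runs on from treatment and visit to "visit*treatment, actual reversibility strata (reversible, non-reversible"), but the section opens by deferring: "For details of their inclusion in the models, see the specific analysis section".

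The stratum does appear in these models:
- the sensitivity ANCOVA (SAP 16.5; protocol 9.4.5 has "fixed factors for treatment, reversibility strata and the pre-dose baseline value as a covariate")
- the AUC0-12h and IC ANCOVAs and the CAT responder model (SAP 16.3.2)
- the SGRQ-C responder model (SAP 16.2.2)
- the blinded interim ANCOVA (SAP 16.6.1)

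It is absent from the blinded interim MMRM (SAP 16.6.2).

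**The concern.** Stratified allocation balances reversibility across arms, so differences between strata add nothing to the sampling variance of a treatment contrast. A model without the stratum does not know this and leaves the between-stratum variance in the residual. Reported standard errors are then too large, confidence intervals too wide, and the nominal 5% tests run below 5%.

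The stratum is a plausible predictor here. The endpoint is the FEV1 peak after an inhaled bronchodilator, the protocol expects reversible patients to respond more, and every arm, placebo included, takes tiotropium just before study medication.

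Three things are at stake:
- **Power.** Testing runs in fixed sequence from 3 mg downwards, so one avoidable non-significant result ends the testing of all lower doses in a trial meant to support dose selection.
- **Specification.** A programmer working from SAP 7.1 and one working from 16.1.2 could fit different primary models.
- **Interpretation.** The primary MMRM and the sensitivity ANCOVA differ in covariates as well as in missing-data handling (the ANCOVA uses LOCF), so a disagreement between them is harder to read.

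**Working it through.** **Inputs from the documents.** SD 200 mL, difference 93 mL, two-sided 5%, 73 evaluable per arm, 80% power (protocol 9.5); two-sample t-test basis (SAP 16.6); strata capped at 50% with equal allocation within stratum (protocol 5.7).

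**Assumptions.** D is the stratum difference in mean peak FEV1 change that remains after baseline FEV1. The documents do not give it, so I use 50 to 200 mL. Strata are taken as exactly 50:50 in every arm.

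**Plan's own figure.** n = 2 × [(1.960 + 0.842) × 200/93]² = 72.6, so 73 per arm. With k = √(2/73) = 0.1655, the SE is 200k = 33.1 mL and power is Φ(93/33.1 − 1.96) = 80.2%. The plan's figure reproduces.

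**(1) 200 mL is the SD before stratum adjustment**, as the two-sample t-test basis suggests. The residual SD within strata is r = √(200² − (D/2)²). Under either model the estimate has true SD r·k. The rejection cut-off is 1.96 × 200k = 64.9 mL without the stratum and 1.96·r·k with it. Power = Φ((93 − cut-off)/(r·k)). Actual alpha without the stratum = 2[1 − Φ(1.96 × 200/r)].

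| D (mL) | r (mL) | SE overstated by | Power without | Power with | Alpha without |
|---|---|---|---|---|---|
| 50 | 198.4 | 0.8% | 80.4% | 80.8% | 4.8% |
| 100 | 193.6 | 3.3% | 81.0% | 82.7% | 4.3% |
| 150 | 185.4 | 7.9% | 82.0% | 85.8% | 3.4% |
| 200 | 173.2 | 15.5% | 83.7% | 90.0% | 2.4% |

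The gain passes one percentage point at D of about 77 mL.

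**(2) Baseline FEV1 absorbs half of the between-stratum variance.** Replace D by D√0.5. Raw differences of 50, 100, 150 and 200 mL then give gains of 0.21, 0.85, 1.91 and 3.35 points.

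**(3) D differs by arm, overall SD 200 mL.** The within-stratum SD is w = √(200² − mean(Dₐ²)/4). A model with one common stratum term has SD √(w² + mean((Dₐ − D̄)²)/4). The true SD of the estimate is w·k.
- Placebo 0, actives 100: w = 194.9, adjusted SD 196.0, power 80.8% without and 81.9% with.
- Placebo 50, actives 150: w = 188.1, adjusted SD 189.1, power 81.7% without and 84.5% with.

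**(4) 200 mL is already net of the stratum.** The SD without the stratum is √(200² + (D/2)²) = 201.6, 206.2, 213.6 and 223.6 mL, and the true SD of the estimate is 200k. Power without the stratum is 79.8%, 78.5%, 76.3% and 73.2%, against 80.2% with it.

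**Simulation.** 10,000 runs per setting, five arms of 74 (37 per stratum), one visit, scenario (1). Without the stratum, null rejection was 4.6%, 4.2%, 3.6% and 2.2% for D = 50 to 200. With it, rejection was 4.8% to 5.2%. The mean reported SE without the stratum stayed at about 32.9 mL, while the true SD of the estimate fell to 32.5, 31.9, 30.7 and 28.3 mL.

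**The case against.** **The SAP may intend the stratum.** The list in SAP 7.1 reads like an MMRM specification, because visit, the visit-by-treatment interaction and random patient belong to no other kind of model in the document. That is a fair reading. But 7.1 hands the decision to the specific section, and 16.1.2 and protocol 9.4.5 agree on leaving the stratum out, so omission is the operative reading. The mismatch needs resolving either way.

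**There is no harm to validity, and the loss may be slight.** This stands. In scenario (1) power never falls below the planned 80%, so what is lost is forgone power. D = 100, 150 and 200 mL require the stratum to explain 6%, 14% and 25% of the variance left after baseline ((D/2)²/200²), and D = 150 exceeds the 93 mL target difference. If reversible patients mainly respond more to study drug, the placebo 0 / actives 100 case is closest, and the gain there is about one point. Scenario (4) rests on a reading of the 200 mL that the documents do not support.

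**The alpha figures assume perfect balance.** Also correct. The protocol promises only approximately equal numbers, and withdrawals will disturb the balance; any imbalance reduces the conservatism. The simulation covers a single visit, not the planned MMRM.

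**Other analyses cover it.** The stratum-adjusted ANCOVA (SAP 16.5) and the separate reversibility models (SAP 7.4, 16.1.2) help, but they do not replace the primary test.

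**Breadth and choice of stratum.** The figures concern peak FEV1 only; nothing in the documents shows that reversibility predicts the symptom scores or rescue use. SAP 10 reports planned and actual reversibility separately, so the two can differ, and the balance argument strictly concerns the stratum used at randomisation. Using the actual stratum follows the SAP's own convention.

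**Conclusion.** The concern holds. The primary MMRM as written omits the stratification factor, the MMRMs that refer to it inherit the omission, and SAP 7.1 does not match 16.1.2. The treatment estimate is unbiased and type I error is not inflated. If the stratum predicts peak FEV1 change beyond baseline, the reported SEs are too large and the tests conservative.

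Under scenario (1) the power forgone is under 2 points for D up to 100 mL, about 4 points at 150 mL and about 6 points at 200 mL. These figures rest on an assumed D, 50:50 strata balanced across arms, and 200 mL being the SD before stratum adjustment. The true size is unknown and may be small. The change is still worth making, because it costs almost nothing and the specification has to be reconciled anyway.

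**What to change.** Before unblinding:

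1. Add the actual reversibility stratum, as used in SAP 7.1 and 16.5, as a fixed effect in the SAP 16.1.2 MMRM and in the MMRMs that refer to it. Leave it out of the reversibility subgroup models, which are fitted separately by stratum.
2. State explicitly that the actual rather than the randomised stratum is used.
3. Reconcile SAP 7.1, SAP 16.1.2 and protocol 9.4.5.
4. Record the change in SAP 3.3, which now says that none is planned, and justify it in the clinical study report as protocol 9.1 requires.
5. Add the term to the blinded interim MMRM (SAP 16.6.2) only if that analysis has not been run. It may have been: the planned study period ended in November 2019 and the SAP is dated 05DEC2019.

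The cost is one degree of freedom and a documented change to a protocol-specified primary model. No new data are needed, because SAP 10.1 already derives the actual stratum.

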The standard deviation for peak FEV₁ is estimated to be 200 mL. With a 2-sided test at a 5% significance level and 73 evaluable patients per group, there will be 80% power to detect a true difference of 93 mL between any two treatments. This detectable limit has been considered sufficient to identify an effective dose of RPL554. Assuming a 10% early withdrawal rate, 80 patients per group will be randomized.

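### The primary MMRM fits one baseline FEV₁ slope from Day 1 to Week 4; if that slope changes over time, the Week 4 comparison may lose a little precision, which a baseline-by-visit term would recover at negligible cost

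*SAP*

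**What the plan says.** SAP 16.1.2 compares treatments on change from baseline FEV₁ to peak FEV₁ with "fixed effects for treatment, visit and treatment by visit interaction, patient as random effect and baseline as covariate". Protocol 9.4.5 has the same terms: "treatment, visit and treatment by visit interaction, baseline as covariate, patient as random and covariance structure by visit". SAP 7.1 lists five visits (Day 1 and Weeks 1 to 4) and names treatment-by-visit as the only interaction.

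Baseline FEV₁ "is the latest measurement taken before study drug on the day of first dosing, i.e. 30 minutes pre-dose at Day 1". The peak is the maximum in the 3 hours after dosing. On the covariance, SAP 16.1.2 states: "An unstructured covariance structure will be used to model the within-patient errors", with compound symmetry as the fallback.

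SAP 16.2.2 applies the same approach, "as described in Section 16.1.2 for the primary endpoint", to the secondary spirometry, diary and questionnaire endpoints. SAP 16.5 adds a Week 4 ANCOVA with LOCF as a sensitivity analysis.

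**The concern.** The Day 1 peak is read within hours of baseline and the Week 4 peak four weeks later. A same-day reading would be expected to follow baseline more closely, so the regression of change on baseline may be flatter on Day 1 than at Week 4. The model allows only one slope. Generalised least squares with an unstructured covariance gives most weight to the least variable visit, which may well be Day 1. The Week 4 contrast could then be adjusted with a slope that is not the Week 4 slope.

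What is at stake is precision. Chance baseline imbalance would be removed less completely from the primary contrast. The sample size leaves no reserve above 80% power, and the fixed sequence from 3 mg downward stops at the first non-significant dose.

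**Working it through.** **The plan's own figure.** Protocol 9.5 gives SD 200 mL, difference 93 mL, two-sided 5% and 80% power. The normal formula gives n = 2(1.960 + 0.842)² × 200² / 93² = 72.6, so 73 per group, as stated. Power at n = 73 is 80.2% by the normal formula and 79.7% by the noncentral t. The noncentral t is used below.

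**Inputs not in the documents (assumed).** Baseline SD S = 300–600 mL; residual SD given baseline 130 mL on Day 1 and 200 mL at Weeks 1–4; residual correlation ρ = 0.6–0.75 between all visits; total SD of peak FEV₁ equal to f × S at every visit, with f = 1.0–1.1.

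**Step 1: slope at each visit.** With residual SD r, the slope of change on baseline is b = f√(1 − (r/(fS))²) − 1. For S = 400, f = 1.0:
- Day 1: √(1 − (130/400)²) − 1 = −0.054
- Week 4: √(1 − (200/400)²) − 1 = −0.134
- Difference Δ = 0.080

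**Step 2: common slope.** With complete data and saturated treatment-by-visit means, the common slope is the generalised least-squares average of the visit slopes. Weeks 1–4 share one slope here, so the weight on Day 1 is w = (V_L − C)/(V_1 + V_L − 2C), where V_1 = 130² = 16,900, V_L = 200²(1 + 3ρ)/4 and C = ρ × 130 × 200.
- ρ = 0.6: V_L = 28,000, C = 15,600, w = 12,400/13,700 = 0.905
- ρ = 0.75: V_L = 32,500, C = 19,500, w = 13,000/10,400 = 1.25

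A weight above 1 means that the common slope overshoots the Day 1 slope.

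**Step 3: cost at Week 4.** The gap between the Week 4 slope and the common slope is wΔ. The Week 4 residual variance is multiplied by 1 + S²(wΔ)²/200². For S = 400, ρ = 0.75: gap 1.25 × 0.080 = 0.100, and (400 × 0.100)²/200² = 4.0%.

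| S (mL) | f | Δ | Gap, ρ 0.6 / 0.75 | Variance rise | Power |
|---|---|---|---|---|---|
| 300 | 1.0 | 0.156 | 0.141 / 0.195 | 4.5% / 8.5% | 77.9% / 76.4% |
| 400 | 1.0 | 0.080 | 0.072 / 0.100 | 2.1% / 4.0% | 78.9% / 78.1% |
| 600 | 1.0 | 0.033 | 0.030 / 0.042 | 0.8% / 1.6% | 79.4% / 79.1% |
| 600 | 1.1 | 0.030 | 0.027 / 0.038 | 0.7% / 1.3% | 79.4% / 79.2% |

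With Day 1 residual SD 160 mL the rise is 0.1% to 1.6%. With 200 mL on Day 1 as well, Δ = 0 and there is no loss. A Day 1 SD below 130 mL combined with correlation 0.75 would push the top of the range above 8.5%.

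**Simulation** (five arms of 73, complete data, baseline SD 500 mL, 3,000 replicates per setting). Standard error of the Week 4 contrast, common slope against slope by visit:
- Equal slopes: 32.9 against 33.0.
- Slopes running from −0.03 to −0.13: 34.0 against 33.3 (power 78.5% against 80.2%).

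The mean estimate was about 92–94 mL under both models in every setting, against a true 93 mL.

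**The case against.** The case for leaving the model alone has several parts.

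- **The loss is conditional.** Nothing in the documents shows that the slopes differ or that Day 1 is quieter. This stands, and the point is worded accordingly.
- **The 80% benchmark is itself an assumption.** Protocol 9.5 says only that the SD "is estimated to be 200 mL". If that figure came from a common-slope model, the loss is already in the sample size. This also stands.
- **The plan has other checks.** The blinded re-estimation in SAP 16.6 fits both a Visit 6 ANCOVA and a common-slope MMRM and compares each SD with 200 mL. However, an 8.5% rise in variance is only a 4.2% rise in SD (√1.085 = 1.042), well inside the 12% that SAP 4.2 tolerates. The Week 4 ANCOVA fits its own slope but is an LOCF sensitivity analysis. Neither changes the primary model.
- **The pull toward Day 1 needs the unstructured covariance.** Under the compound-symmetry fallback all visits would weigh equally with complete data. That is the fallback, not the plan.

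Two stronger readings are tempting. A reader might take a slope gap of 0.20 and baseline SD 450 mL and infer a variance rise of about 30%, worth some 22 patients per arm (0.30 × 73), with power near 69%. Those inputs do not fit together: at baseline SD 450 mL, the residual SDs above imply a slope difference of only 0.055–0.062. A difference of 0.20 would need the total SD of peak FEV₁ to shrink from 450 to about 395 mL by Week 4. A reader might also infer that nearly all secondary endpoints are affected, because the model is reused. The Day 1 argument reaches only the peak and AUC endpoints: trough, E-RS and rescue use start at Week 1, SGRQ-C and TDI at Week 2, and the PGAC model has no baseline term.

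**Conclusion.** The specification is as described, and the mechanism is real but conditional. If the baseline slope differs between Day 1 and Week 4 and Day 1 is the less variable visit, the primary contrast may lose some precision. Under the assumed SDs and correlations, the Week 4 variance rises by about 1% to 8.5%, equivalent to roughly 1 to 6 patients per arm (0.007 × 73 = 0.5; 0.085 × 73 = 6.2). Power falls from about 80% to between 79% and 76%. With equal slopes the loss is zero. The documents do not show that precision is in fact lost, and nothing here threatens validity: randomisation keeps the Week 4 contrast unbiased under either model. The calculations assume complete data; dropout was not modelled. Severity: minor.

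**What to change.** Add a baseline-by-visit interaction to the MMRM in SAP 16.1.2 and to the peak and AUC MMRMs that refer to it. Estimate the Week 4 treatment differences from that model at the overall mean baseline. Make the matching change in Protocol 9.4.5, or record it in SAP 3.3, which currently declares no changes from the protocol.

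The cost is four extra parameters with five visits. With about 365 evaluable patients (5 × 73), the critical t moves from 1.9666 to 1.9667 and the standard error rises by about 0.2% if the slopes are equal. No data collection or sample size changes.
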